6.2.3.3 Assessment of non-target lesions by iRECIST

The iRECIST assessment of non-target lesions at each timepoint follows similar principles to evaluation of the iRECIST target lesions. iUPD (but not iCPD) can have been documented before iCR or when the criteria for neither CR nor PD have been met (referred to as non-iCPD/non-iUPD) and can be assigned several times, as long as iCPD was not confirmed. iUPD is defined by RECIST 1.1 criteria; however, iUPD can be assigned multiple times as long as iCPD is not confirmed at the next assessment. Progressive disease in the non-target lesion category is confirmed if subsequent imaging, done 4-8 weeks after iUPD, shows a further increase from iUPD. The criteria for iCPD are not judged to have been met if RECIST 1.1 criteria for complete response or non-iCR/non-iUPD are met after a previous iUPD. The status is reset (unlike RECIST 1.1) and iCR, or non-iCR/non-iUPD is assigned; if no change is detected, the timepoint response is iUPD.)

6.2.3.4 Assessment of Best overall Response by iRECIST

For iRECIST, the best overall response (iBOR) is the best timepoint response recorded from the start of the study

treatment until the end of treatment, taking into account any requirement for confirmation. iUPD will not override a subsequent best overall response of iSD, iPR, or iCR, meaning that iPR or iSD can be assigned (timepoint response or iBOR) even if new lesions have not regressed, or if unequivocal progression (non-target lesions) remains unchanged, providing that the criteria for iCPD are not met.

6.2.4 Image Acquisition

6.2.4.1 CT Exam Acquisition

Recognizing that this protocol is collecting standard of care (SOC) imaging, the following imaging parameters have been chosen as a guide to accommodate a variety of Multi-Detector CT Scanners. It is recommended that the imaging studies be acquired in full inspiration.

Series	Guideline
Scout/Topogram	
• 100 kv• 10-40 mA• Acquire on inspiration
Axial	
• Slice Thickness/Spacing: Standard of Care• mA: As Low As Reasonably Attainable• Dose Modulation: On – if available• Acquire on Inspiration
Post Processing Reconstructions from Raw Data	
• Axial Plane (Optional)
• Slice Thickness: 1mm• Slice Spacing: 1mm• Soft Tissue Algorithm (Kernel)• Bone/Lung Algorithm (Kernel)• Sagittal Plane (optional)
• Slice Thickness: 1mm• Slice Spacing: 1mm• Soft Tissue Algorithm (Kernel)• Bone/Lung Algorithm (Kernel)• Coronal Plane (optional)
• Slice Thickness: 1mm• Slice Spacing: 1mm• Soft Tissue Algorithm (Kernel)• Bone/Lung Algorithm (Kernel)

6.3 Submission of Images for Central Review

- 6.3.1 Each participating site is required to submit all acquired diagnostic and follow-up images of study participants to the ACR Imaging Core Laboratory. Imaging should be submitted to the ACR Imaging Core Lab via TRIAD 4 and any associated data forms should be completed within 48 hours of acquisition. Prompt submission of all image data is essential to ensure adequate image quality assessment.
- 6.3.2 TRIAD® is ACR's proprietary image exchange application that will be used as the sole method of data transfer to the ACR Clinical Research Center Core Laboratory for this trial. The TRIAD application can then be configured as a DICOM destination on either scanner(s) and/or PACS system for direct network transfer of study related images into the TRIAD directory.

TRIAD Access Requirements:

- Staff who will submit images through TRIAD will need to be registered with The Cancer Therapy Evaluation Program (CTEP) and have a valid and active CTEP Identity and Access Management (IAM) account. Please refer to the beginning of Section 4 for instructions on how to request a CTEP-IAM account.
- To submit images, the user must be assigned the 'TRIAD site user' role on the relevant Group or CTSU roster. ECOG-ACRIN users should contact your site Lead RA to be added to your site roster.

TRIAD Installations:

When a user applies for a CTEP-IAM account with proper user role, he/she will need to have the TRIAD application installed on his/her workstation to be able to submit images. Support and information on installation of TRIAD can be found at <https://triadhelp.acr.org/clinicaltrials>. The TRIAD helpdesk can be reached at [contact]. This process can be done in parallel to obtaining your CTEP-IAM account username and password.

7. Therapeutic Parameters

7.1 Step 1: Therapeutic Parameters

Treatment should start within seven working days after registration (see Section 5)

	Screening ¹	Cycle 1 ^{1,2} (day 1)	Cycle 1 mid ² (day 15)	Cycle 2 ² (day 29)	Cycle 2 mid ² (day 43)	Cycle 3+ ² (day 57)	Post Treatment Follow Up ³
History and physical exam ⁵	X	X	X	X	X	X	X
Performance status, vital signs ⁵	X	X	X	X	X	X	
Complete blood count with differential ⁶	X		X	X	X	X	
Blood chemistry tests ⁷	X		X	X	X	X	
PT/INR and PTT	X						
Thyroid tests (TSH and reflex free T4) ⁴	X			X		X	
Electrocardiogram (ECG) ⁴	X			X		X	
Echocardiogram/MUGA ⁸	X						
Urine protein assessment ⁹	X			X		X	
Serum or Urine Pregnancy Test ¹⁰	X						
Toxicity Assessment		X	X	X	X	X	X
Tumor assessment imaging ^{11,16}	X					X ¹¹	X ³
Brain Imaging ¹²	X ¹²					X ¹²	
Nivolumab (Arms A, B, C, T)		X		X		X	
Cabozantinib (Arms B, C, T) ¹⁸		X	X	X	X	X	
Ipilimumab (Arm C)		X				X ¹⁵	
MANDATORY: Tumor Tissue ¹⁴	X						
Tobacco Use Assessment PROs ¹⁷							See Section 5.6

Cycle Length = 28 days

1. All baseline assessments must be done \leq 2 weeks before registration with the exception of imaging studies that must be done \leq 4 weeks before registration and brain imaging studies that must be done \leq 12 weeks before registration in patients without known brain metastases. Patients

with known brain metastases at baseline must have a brain MRI or head CT with contrast \leq 4 weeks prior to registration. All baseline laboratory tests can be used for Cycle 1 Day 1 treatment purposes.

2. Window for study visits and drug administration is \pm 3 days. Mid-cycle 1 and 2 visits are required for all arms. Starting with cycle 3, in-person visit by investigator is only required once per cycle.

NOTE: All hematology and chemistry assessments must be done \leq 72 hours prior to day 1 of the treatment cycle except for Cycle 1 Day 1 (see footnote 1).

3. Every 3 months until patient is 5 years from registration. Physical exam not required. If in person visit is not possible, patient should be contacted for follow up of vital status and assessment of any study-related toxicities until resolution. For patients that discontinued study therapy prior to radiographic progressive disease, tumor assessments should be performed at least every 3 months during long term follow up until progressive disease is documented.

- Rev. Add4
4. Screening TSH and reflex free T4 to be done only if clinically indicated. Every cycle (4 weeks) for these tests. ECG, TSH and reflex free T4 for all arms. ECG required to monitor patients on cabozantinib containing arms for QTcF \leq 500 msec, and monitor for evidence of myocarditis on all arms.
 5. Smoking status and height are to be collected once prior to treatment. ECOG performance status. Vital signs include heart rate, blood pressure, O₂ saturation, respiratory rate, and weight.
 6. CBCs (with differential and platelet count) includes WBC, ANC, Platelets, Hgb, and Hct and must be done \leq 72 hours prior to day 1 of the treatment cycle, except for Cycle 1 Day 1 they may be performed within 2 weeks of registration.
 7. Blood chemistry tests include measurement of magnesium and phosphorus plus comprehensive metabolic panel (ALT, AST, alkaline phosphatase, bilirubin, creatinine, blood urea nitrogen, calcium, sodium, potassium, albumin, chloride, and bicarbonate (or CO₂). All blood chemistries must be done \leq 72 hours prior to day 1 of the treatment cycle, except for Cycle 1 Day 1 they may be performed within 2 weeks of registration.
 8. Baseline Echocardiogram OR MUGA to evaluate ejection fraction to be performed during screening ONLY as clinically indicated - in patients with a history of CHF or at risk because of underlying cardiovascular disease or prior exposure to cardiotoxic drugs.
 9. Urine protein analysis required at screening, then only for patients receiving cabozantinib (Arms B, C, T). Urine dipstick at baseline must be < 1 + (0 or "trace") or Urine Protein Creatinine (UPC) must have been performed. If urine dipstick results are \geq 1+, UPC ratio is clinically indicated and Section 5 should be referred to for management.
 10. Women of childbearing potential only. All women of childbearing potential must have a negative pregnancy test \leq 2 weeks before registration.
 11. All efforts must be made to assess tumor from the same type of scan that was performed at baseline. A CT scan with contrast involving known systemic areas of disease is recommended. Imagine studies should be done within 4 weeks prior to registration and every 8 weeks (based on Cycle 1 Day 1) during treatment until PD. The imaging should be done within 7 days prior to cycle 3, 5, 7, 9 etc. but may be performed after the treatment for unusual circumstances such as holidays. If drugs are held, the imaging should still be performed every 8 weeks counting from Cycle 1 Day 1.
 12. Patients must have a brain MRI or head CT with contrast at baseline within 12 weeks prior to registration. Patients with known brain metastases at baseline must have a brain MRI or head CT within 4 weeks prior to registration. Patients with known brain metastases should have repeat imaging at least every 16 weeks (4 cycles). Repeat brain imaging is not required for patients without known brain metastases at baseline.
 13. Tumor tissue specimens are required to be submitted for defined laboratory research studies as outlined in Section 10.
 14. All specimens submitted must be entered and tracked via the online ECOG-ACRIN Sample Tracking System (STS).

15. Ipilimumab administration every 8 weeks (cycle 1, 3, 5, 7, etc.)
16. For Arm T patients, to be assigned a status of complete or partial response, changes in tumor measurements must be confirmed by repeat assessments performed no less than four weeks after the criteria for response are first met. Arm A, B, and C patients do not require confirmation scans for complete or partial response.
17. Tobacco use assessment PROs will be collected using EASEE-PRO.
18. Oral daily dosing

Rev. Add4

8. Drug Formulation and Procurement

This information has been prepared by the ECOG-ACRIN Pharmacy and Nursing Committees.

Availability

Drug Ordering: Bristol-Myers Squibb and Exelixis are supplying Nivolumab, Ipilimumab, and Cabozantinib, through the Division of Cancer Treatment and Diagnosis, NCI, for this protocol. Maintenance of NCI drug accountability records is required. Drugs may be requested by the Principal Investigator (or their authorized designees) at each participating institution. Pharmaceutical Management Branch (PMB) policy requires that drug be shipped directly to the institution where the patient is to be treated. PMB does not permit the transfer of agents between institutions (unless prior approval from PMB is obtained – see general information). The CTEP-assigned protocol number must be used for ordering all CTEP-supplied investigational agents. The responsible investigator at each participating institution must be registered with CTEP, DCTD through an annual submission of FDA Form 1572 (Statement of Investigator), NCI Biosketch, Agent Shipment Form, and Financial Disclosure Form (FDF). If there are several participating investigators at one institution, CTEP-supplied investigational agents for the study should be ordered under the name of one lead investigator at that institution.

No starter supplies will be provided. Study agents must be ordered after the patient is enrolled on the assigned treatment arm. If expedited shipment is required, sites should provide an express courier account through the Online Agent Order Processing (OAOP) application.

Submit agent requests through the PMB Online Agent Order Processing (OAOP) application (<https://ctepcore.nci.nih.gov/OAOP>). Access to OAOP requires the establishment of a CTEP Identity and Access Management (IAM) account (<https://eapps-ctep.nci.nih.gov/iam>) and the maintenance of an “active” account status and a “current” password. For questions about drug orders, transfers, returns, or accountability, call or email PMB any time. Refer to the PMB’s website for specific policies and guidelines related to agent management.

NCI Supplied Agent(s) – General Information

Questions about drug orders, transfers, returns, or accountability should be addressed to the PMB by calling [contact] Monday through Friday between 8:30 AM and 4:30 PM Eastern Time or email [contact] anytime.

Drug Returns: All unused drug supplies must be returned to the PMB. When it is necessary to return study drug (e.g., sealed vials remaining when a patient permanently discontinues protocol treatment, expired vials recalled by the PMB), investigators must return the study drug to the PMB using the NCI Return Agent Form available on the NCI home page (<http://ctep.cancer.gov>) or by calling the PMB at [contact].

Agent Inventory Records: The investigator, or a responsible party designated by the investigator, must maintain a careful record of the receipt, dispensing and final disposition, of all agents received from the PMB using the appropriate NCI Investigational Agent (Drug) Accountability Record (DARF) available on the CTEP forms page. Store and maintain separate NCI Investigational Agent Accountability Records for each agent, strength, formulation and ordering investigator on this protocol.

Investigator Brochure Availability: The current versions of the IBs for the agents will be accessible to site investigators and research staff through the PMB Online Agent Order Processing (OAOP) application. Access to OAOP requires the establishment of a CTEP Identity and Access Management (IAM) account and the maintenance of an "active" account status and a "current" password. Questions about IB access may be directed to the PMB IB coordinator via email.

Useful Links and Contacts

- CTEP Forms, Templates, Documents: <http://ctep.cancer.gov/forms/>
- NCI CTEP Investigator Registration: [contact]
- PMB policies and guidelines: http://ctep.cancer.gov/branches/pmb/agent_management.htm
- PMB Online Agent Order Processing (OAOP) application: <https://ctepcore.nci.nih.gov/OAOP>
- CTEP Identity and Access Management (IAM) account: <https://ctepcore.nci.nih.gov/iam/>
- CTEP IAM account help: [contact]
- PMB email: [contact]
- IB Coordinator: [contact]

PMB phone and hours of service: [contact] Monday through Friday between 8:30 am and 4:30 pm (ET)

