2.2 Secondary Endpoints

- 2.2.1 To estimate the overall survival for each arm of the trial
- 2.2.2 To estimate the best overall response rate for each arm of the trial
- 2.2.3 To estimate the progression free survival of the targeted therapy arm of the trial
- 2.2.4 To describe the toxicity profile of monotherapy with nivolumab, and the combination of nivolumab and cabozantinib, and the combination of nivolumab and cabozantinib and ipilimumab, in this patient population with non-squamous NSCLC.

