 - Screening urine dipstick must equal 0 or "trace." If urine dipstick results are $\geq 1+$, or if dipstick was not performed, calculation of Urine Protein Creatinine (UPC) is required and patients must have a UPC ratio ≤ 1 to participate in the study.
Urine dipstick = 0 or "trace?" (Yes/No) _____ Date of test _____
If no, UPC ratio ≤ 1 ? (Yes/No) _____ Date of test _____

- _____ 3.2.15 No history of the following:
- Clinically-significant gastrointestinal bleeding within 6 months prior to registration.
 - Hemoptysis of ≥ 0.5 teaspoon (2.5 mL) of red blood within 3 months prior to registration.
 - Drug induced pneumonitis within 3 months prior to registration
 - Signs indicative of pulmonary hemorrhage within 3 months before the first dose of study treatment
 - Radiographic evidence of cavitating pulmonary lesion(s)
 - Tumor invading any major blood vessels
 - Evidence of tumor invading the GI tract (esophagus, stomach, small or large bowel, rectum or anus), or any evidence of

- endotracheal or mainstem endobronchial tumor within 28 days before the first dose of cabozantinib
- _____ 3.2.16 No concomitant anticoagulation with oral anticoagulants (eg, warfarin, direct thrombin and Factor Xa inhibitors) or platelet inhibitors (eg, clopidogrel). Allowed anticoagulants are the following:
- Low-dose aspirin for cardioprotection (per local applicable guidelines) is permitted.
 - Low molecular weight heparins (LMWH) or unfractionated heparin is permitted.
 - Anticoagulation with therapeutic doses of LMWH is allowed in subjects without known brain metastases who are on a stable dose of LMWH for at least 6 weeks before first dose of study treatment, and who have had no clinically significant hemorrhagic complications from the anticoagulation regimen or the tumor.
- _____ 3.2.17 No concomitant treatment of strong CYP3A4 inducers (e.g., dexamethasone, phenytoin, carbamazepine, rifampin, rifabutin, rifapentine, phenobarbital, and St. John's Wort).
- _____ 3.2.18 No cardiovascular disorders including:
- a) Congestive heart failure (CHF): New York Heart Association (NYHA) Class III (moderate) or Class IV (severe) at the time of screening
 - b) Concurrent uncontrolled hypertension defined as sustained BP > 150 mm Hg systolic, or > 100 mm Hg diastolic despite optimal antihypertensive treatment within 7 days prior to registration
 - c) Any of the following within 6 months prior to registration:
 - unstable angina pectoris
 - clinically-significant cardiac arrhythmias

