 - stroke (including TIA, or other ischemic event)
 - myocardial infarction
- _____ 3.2.19 No gastrointestinal disorders associated with a high risk of perforation or fistula formation within 3 months prior to registration:
- active peptic ulcer disease,
 - inflammatory bowel disease (including ulcerative colitis and Crohn's disease), diverticulitis, cholecystitis, symptomatic cholangitis or appendicitis
 - known malabsorption syndrome
 - bowel obstruction or gastric outlet obstruction
 - PEG tube placement
- _____ 3.2.20 No gastrointestinal disorders associated with a high risk of perforation or fistula formation within 6 months prior to registration:
- abdominal fistula
 - gastrointestinal perforation
 - intra-abdominal abscess. Note: Complete resolution of an intra-abdominal abscess must be confirmed prior to initiating treatment

with cabozantinib even if the abscess occurred more than 6 months prior to registration.

- _____ 3.2.21 None of the following conditions:
- Grade 3 or greater infection, or infection requiring intravenous systemic treatment within 28 days prior to registration. Patients should be off antibiotics at the time of registration.
 - serious non-healing wound/ulcer/bone fracture within 28 days prior to registration
 - history of organ transplant
 - concurrent symptomatic untreated hypothyroidism within 7 days prior to registration
 - history of surgery as follows:
 - Major surgery (as an example, surgery requiring anesthesia and a > 24 hour hospital stay) within 3 months prior to registration , with wound healing at least 28 days prior to registration.
 - Minor surgery within 28 days prior to registration with complete wound healing at least 10 days prior to registration.
 - Minor procedures within 7 days prior to registration such as thoracentesis, paracentesis, or 18g or smaller needle biopsy of tumor
 - Patients with clinically relevant ongoing complications from prior surgery are not eligible.
- _____ 3.2.22 Patients must have corrected QT interval calculated by the Fridericia formula (QTcF) \leq 500 ms within 28 days before registration.
QTcF = QT divided by cube root of the RR interval (QT/RR^{0.333})
- _____ 3.2.23 Patients must be able to swallow tablets.
- _____ 3.2.24 No currently active other malignancies which require systemic treatment

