9.3 Statistical Analysis Plan

The primary and some secondary analyses will include all eligible and treated patients. Exceptions to this include: analysis of toxicity data, which will include all patients who received study drug regardless of eligibility, and analyses of response, which will include eligible and treated patients with measurable and evaluable disease.

Time-to-event data, such as PFS and OS, will be estimated using the Kaplan-Meier method, and Cox proportional hazards models will be used to estimate the treatment hazard ratios. The primary comparison of PFS will use a logrank test stratified on the randomization stratification factors with a one-sided type I error rate of 10%. Other comparisons of groups will be made using the logrank test and Cox modeling.

Categorical data, such as response rates (CR+PR) and toxicity, will be compared using Fisher's exact tests with a one-sided type I error rate of 10%; multivariable logistic regression modeling will be used to adjust for the effect of any covariates that are associated with these categorical outcomes. Though none are currently planned, any continuous outcomes will be analyzed using Wilcoxon rank sum test, and multivariable linear regression models may be used to adjust for multiple associations with outcome.

Modeling procedures will implement backward selection; variables significant at the 0.10 level in the univariate setting will be chosen for inclusion in an initial full model, and at each step the least significant variable will be removed from the model. Only those covariates with $p < 0.05$ will remain in any final models, unless there are factors identified by the study team as crucial to model interpretation.

Point estimates of all endpoints will be accompanied by the corresponding two-sided 80% confidence intervals.

In the event that there are missing data, no imputation of the missing data will be conducted. We will assume that data are missing at random and will conduct all analyses as originally planned because we do not anticipate an excess of missing data.

Subset analyses are planned for all stratification factors and all known prognostic factors, such as performance status, age, sites of metastases, gender, etc. Subset analyses of all variables, including correlatives, are considered to be exploratory in nature.

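### Urine protein is scheduled after screening only in the cabozantinib arms, so proteinuria in Arm A is not comparable with Arms B or C, yet section 9.3 makes no exception for it when toxicity is tested between arms

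*Combined protocol and SAP*

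**What the plan says.** **Urine protein.** The section 7.1 table marks urine protein at screening, cycle 2 and cycle 3 onward. Footnote 9 narrows this: "Urine protein analysis required at screening, then only for patients receiving cabozantinib (Arms B, C, T"). At entry, section 3.2.14 accepts a dipstick of zero or trace; otherwise "patients must have a UPC ratio ≤ 1 to participate in the study". A patient can therefore enter any arm with some proteinuria.

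**Thyroid tests.** Footnote 4 reads "Screening TSH and reflex free T4 to be done only if clinically indicated". It then sets testing every cycle, with "ECG, TSH and reflex free T4 for all arms". The first required value is at cycle 2, day 29. Section 3.2.21 excludes only "concurrent symptomatic untreated hypothyroidism within 7 days prior to registration".

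**Analysis.** Objective 2.2.4 is descriptive: "To describe the toxicity profile of monotherapy with nivolumab" and of the two combinations. Section 9.3 goes further. It groups toxicity with response as categorical data that "will be compared using Fisher's exact tests with a one-sided type I error rate of 10" percent. The toxicity set is everyone who received study drug, eligible or not. No adverse event term is named, none is excepted, and there is no rule for unequal ascertainment or for abnormalities present at baseline.

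**The concern.** Proteinuria is found largely by testing, and here the randomised arm decides whether the test is scheduled. In Arm A a case is recorded only if something else prompts a urine test. If section 9.3 is applied as written, an observed excess in Arm B or C mixes the effect of cabozantinib with the effect of looking for it, and the nominal 10% error rate no longer describes the comparison. The Arm A rate in the toxicity tables would also read as a measured rate when it is not one.

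The thyroid issue is of a different kind. Without a required pre-treatment TSH, an asymptomatic abnormality that was already present may first appear at day 29 and be counted as on-treatment toxicity. This affects how each arm's absolute rate is read.

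**Working it through.** **Inputs from the documents**
- Section 9.4: 129 eligible and treated, 43 per arm; 10% ineligibility; 144 randomised.
- Section 9.3: Fisher's exact test, one-sided 0.10. The direction is not stated; excess on the cabozantinib arm is assumed here.
- Section 1.2 table (phase I, genitourinary tumours), any grade: proteinuria 7/30 = 23% on two drugs and 2/18 = 11% on three; hypothyroidism 17/30 = 57% and 5/18 = 28%.

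**Assumptions not in the documents:** Arm A's true proteinuria rate; the fraction d of its cases detected without scheduled testing; the prevalence b of unmeasured baseline thyroid abnormality; a 10% thyroid incidence in Arm A.

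**Step 1. The plan's own figure.** 129 / 0.90 = 143.3, so 144 randomised and 144 / 3 = 48 per arm. This agrees with section 9.4. The toxicity set therefore holds up to 48 per arm, not 43. The plan gives no figure for proteinuria.

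**Step 2. What the test needs when Arm A records none.** For k events against 0 with 43 per arm, p = C(43,k) / C(86,k).
- k = 3: (43·42·41) / (86·85·84) = 74,046 / 614,040 = 0.121
- k = 4: (43·42·41·40) / (86·85·84·83) = 2,961,840 / 50,965,320 = 0.058

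Four or more events against an observed zero are declared an excess. At 48 per arm, 4 against 0 gives p = 0.059.

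**Step 3. False-positive chance with equal true rates and d = 0.** This is P(X ≥ 4) for X ~ Binomial(43, p). At p = 0.05: 1 − (0.1102 + 0.2494 + 0.2756 + 0.1982) = 0.167.

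**Step 4. Partial detection.** Arm A is given rate d·p and the cabozantinib arm rate p. The rejection probability is summed over all pairs of counts, 43 per arm:

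| True rate, both arms | d = 1 | d = 0.5 | d = 0.25 | d = 0 |
|---|---|---|---|---|
| 3% | 1% | 2% | 3% | 4% |
| 5% | 2.5% | 6% | 10% | 17% |
| 11% | 5% | 21% | 39% | 71% |

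At 48 per arm the d = 0 column becomes 6%, 22% and 79%. With equal testing (d = 1) every row is below 10%. The 11% row borrows a cabozantinib-combination rate for Arm A and is an upper illustration.

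**Step 5. Thyroid.** Observed rate = b + (1 − b) × incidence, with the same b expected in each randomised arm.
- Equal incidence of 10% or 28%, b from 0 to 15%: false-positive chance 5% to 7.5%, so no between-arm error arises.
- Absolute rate: at b = 10%, a 10% incidence reads as 0.10 + 0.90 × 0.10 = 19%.
- Contrast: 10% against 28% shrinks from 18 to 0.90 × 18 = 16.2 points, and power at 43 per arm falls from 0.74 to 0.56.

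**The case against.** The strongest reply is that the expected difference is real. Section 5.4.3 rates proteinuria as a known cabozantinib effect and as infrequent for immune therapy, and the nivolumab adverse event list in section 5.3.2 does not include it. Monitoring aimed at the drug that carries the risk is a legitimate choice. At the phase I two-drug rate, about 10 events in 43 would still pass at 10% against 1, 2, 3 or 4 in a fully tested Arm A (p = 0.004, 0.013, 0.034, 0.071). A reader might infer that a cabozantinib excess would be an artefact; the documents do not support that. Nor does any count of four or more pass whatever Arm A's true rate, because that result requires an observed zero: 5 against 1 gives p = 0.101.

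Arm A's kidneys are not unwatched. Creatinine, urea nitrogen and albumin are scheduled in every arm. Section 9.3 does not name proteinuria, and section 5.2.2 leaves what is routinely collected to a forms packet that is not in the documents. Grade 3 proteinuria in the phase I table was only 1/30 and 0/18. All of this stands and limits the point. It does not make the Arm A rate comparable.

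Other stronger readings also fail:
- *The missing baseline TSH biases arm comparisons.* On-treatment testing is the same in all arms and screening precedes randomisation, so it cannot favour an arm.
- *Hypothyroidism cannot be separated from prior disease.* History and examination are required at screening, TSH is drawn when indicated, and symptomatic untreated disease is excluded. Only asymptomatic, undiagnosed abnormality is missed.
- *A pooled worst-grade comparison between arms is contaminated.* Section 9.3 plans none. The only worst-grade analysis is in the Appendix VIII tobacco study, by smoking and exposure across eight trials.

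**Conclusion.** The point holds for proteinuria in Arm A against Arms B or C, and only there. The direction is clear: unscheduled testing lowers Arm A's recorded rate. The size is not known. It is negligible if true proteinuria on nivolumab alone is about 3% (4% false-positive chance with no detection, within the nominal 10%), exceeds nominal at 5% (17%), and is large at 11% (71%). These figures assume equal true rates, 43 per arm and no detection in Arm A; partial detection lowers them. The documents place nivolumab toward the low end, so the main loss is a misleading Arm A rate and a test whose error rate cannot be stated.

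The thyroid point is one of labelling: absolute rates in every arm may be raised, and true contrasts diluted, by an amount the documents do not allow one to estimate. PFS design, power and the section 9.8.2 safety rules are unaffected.

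**What to change.** 1. **Section 9.3, proteinuria.** Add that it will not be tested between Arm A and Arms B or C. Tabulate Arm A as *not systematically assessed*, with a note that any events shown are unscheduled, clinically prompted findings. B against C may be compared as planned.
2. **Section 9.3, thyroid.** Report events in each arm by whether a baseline TSH was available, and label those without one *on-treatment, baseline unknown*.

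The cost is a few sentences of analysis text and two table footnotes. No new procedure, visit or assay is needed, so the change can still be made although the responses to the Amendment 2 review say that further design changes are no longer being implemented. Extending urine testing to Arm A or requiring a pre-dose TSH would also remove the problem, but each adds a procedure, and the TSH footnote was deliberately revised in Addendum 4. Neither is needed for the reports to be read correctly.
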